
 To evaluate the long-term efficacy of itepekimab compared with placebo on NP size. To evaluate the long-term efficacy of itepekimab compared to placebo on nasal congestion. To evaluate the efficacy of itepekimab compared with placebo on sinus opacification. To evaluate the efficacy of itepekimab compared to placebo on symptoms of CRSwNP. To evaluate the efficacy of itepekimab compared to placebo on sense of smell. To evaluate the efficacy of itepekimab compared to placebo on health-related quality of life. To evaluate the efficacy of itepekimab compared to placebo on sleep disturbance. To evaluate the ability of itepekimab compared to placebo to reduce the risk of worsening/acute sinusitis requiring treatment with SCS or sinus surgery. To evaluate the effect of itepekimab compared to placebo on asthma in the subgroup of participants with comorbid asthma. To evaluate the effect of itepekimab compared to placebo in the subgroup of participants with AERD. 	
 Change from baseline to Week 52 in endoscopic NPS (key secondary). Change from baseline to Week 52 in NCS (key secondary). Change from baseline to Week 24 in opacification of sinuses assessed by CT scan using the LMK score. Change from baseline to Weeks 24 and 52 in the TSS (nasal congestion/obstruction, anterior/posterior rhinorrhea, and loss of sense of smell). Change from baseline to Weeks 24 and 52: 
 Loss of smell severity score using the daily CRSwNP sinonasal symptom eDiary. UPSIT score. Change from baseline to Weeks 24 and 52 in SNOT-22 total score. Change from baseline to Weeks 24 and 52 in PROMIS SD-SF-8b scores. Proportion of participants with CRSwNP requiring SCS or surgery for CRS. Annualized rate of SCS course^a or surgery for CRS during the planned study intervention period. Time to first either SCS or surgery for CRS. Change from baseline to Weeks 24 and 52 in pre-BD FEV1 (in mL) in participants with co-morbid asthma. Change from baseline to Weeks 24 and 52 in ACQ-5 score in participants with co-morbid asthma. Change from the baseline to Week 24 and 52 in NPS and NCS in the subgroup of participants with AERD. Proportion of participants with AERD requiring SCS or surgery for CRS during the planned study intervention period.

Objectives	Endpoints

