
 To evaluate the efficacy of itepekimab compared to placebo. To evaluate the safety and tolerability of itepekimab compared to placebo in participants with CRSwNP. To evaluate the PK of itepekimab. Assessment of immunogenicity to itepekimab over time compared to placebo. 	
 Annualized rate of SCS course or surgery for CRS during the planned study intervention period in participants with AERD. Time to first either SCS or surgery for CRS in participants with AERD. Change from baseline to Weeks 24 and 52 in pre-BD FEV1 (in mL) in participants with AERD. Proportion of NPS responders at Weeks 24 and 52 (defined as participants with improvement by at least 1 point in NPS). Proportion of NPS responders at Weeks 24 and 52 (defined as participants with improvement by at least 2 points in NPS). Incidence of TEAEs, TESAEs, TEAESIs and TEAEs leading to treatment discontinuation. Itepekimab concentration in serum. Incidence of treatment-emergent anti-itepekimab antibody (ADA) responses throughout the study.
Tertiary/Exploratory	

 To evaluate the effect of itepekimab on overall health status, cough, PGIS and PGIC. To evaluate the efficacy of itepekimab compared to placebo in CRSwNP quality of life. To evaluate the effects of itepekimab compared to placebo on total sinus opacification. To evaluate the effect of itepekimab on health care resource use/productivity compared to placebo. To evaluate the early effect of itepekimab compared to placebo on lung function and asthma in the subgroup of participants with co-morbid asthma. 	
 Change from baseline to Weeks 24 and 52 in the EQ-5D index and VAS. Change from baseline to Weeks 24 and 52 in PGIS score for each symptom and for symptoms overall. PGIC score at Weeks 24 and 52 for each symptom and for symptoms overall. Change from baseline to Weeks 24 and 52 in Leicester Cough Questionnaire total score. Proportion of SNOT-22 responders at Weeks 24 and 52 (defined as participants with improvement of at least 8.9 points in SNOT-22). Change from baseline to Week 24 in sinus (all sinuses) percent opacification volume assessed by CT scan. Cumulative number of health care resource utilization by visit type. Change from baseline to Weeks 24 and 52 in WPAI-SHP on overall work impairment and daily activity impairment. Change from baseline to Weeks 4 in pre-BD FEV1.

Objectives	Endpoints

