9.2.2.2 Main analytical approach

The 2 co-primary endpoints will be analyzed with the primary estimand defined according to the following attributes:

- Endpoint: change from baseline to Week 24 in NPS and NCS.
- Intervention condition: itepekimab 300 mg Q2W and itepekimab 300 mg Q4W will be compared to placebo, on top of background therapy.
- Analysis population: intent-to-treat (ITT) population.
- Intercurrent events:
 - The following IEs will be handled with a composite variable strategy. Data after the IE will be assigned to the worst possible score:
 - a) Use of selected prohibited/rescue medication (eg, prohibited biologic therapy) prior to Week 24.
 - b) Nasal/sinus surgery prior to Week 24.

- The following IEs will be handled with a treatment policy strategy. All assessments after starting such IE and before or at Week 24 will be included:
 - a) Use of SCS for any reason.
 - b) Study intervention discontinuation.
 - c) Use of other prohibited/rescue medications prior to Week 24.
- Population-level summary: difference in LS means between itepekimab and placebo from ANCOVA model with change from baseline to Week 24 in NPS and NCS as response variables, intervention group (itepekimab 300 mg SC Q2W, itepekimab 300 mg Q4W, or placebo) and randomization stratification factors (asthma/AERD status and regions) as fixed effects, and the baseline value as covariates. The corresponding 95% CI will be provided along with the p-value. In addition, descriptive statistics including number of participants, mean, SEM, and LS means will be provided for each intervention group.
- Missing data handling.

After applying the rules for IEs, if there is still missing data, then the missing data will be handled as follows:

- For participants who discontinue IMP before Week 24 without use of selected prohibited/rescue medication (eg, prohibited biologic therapy) or nasal/sinus surgery prior to Week 24: MI approach will be used to impute missing endpoint value at Week 24, and this MI will use all participants from the same randomized arm, excluding participants who use selected prohibited/rescue medication (eg, prohibited biologic therapy) or nasal/sinus surgery prior to Week 24.

Each of the imputed complete data will be analyzed by fitting the ANCOVA model. Statistical inference obtained from all imputed data will be combined using Rubin's rule.

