9.2.2.4 Supplementary analyses

Supplementary analyses will be performed, eg, to confirm robustness of the results with respect to the IE handling strategy in addition to the primary estimand. In particular, a supplementary analysis will be performed considering a composite strategy for handling the use of SCS for any reason, the use of selected prohibited/rescue medication (eg, prohibited biologic therapy) and nasal/sinus surgery prior to Week 24 (data after the IE will be assigned to the worst observation carried forward [WOCF]). In addition, a supplementary analysis will be performed considering a treatment policy strategy to handle all the IEs. Details of the supplementary analyses will be provided in the SAP.

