9.2.3 Secondary endpoint(s) analyses

The secondary endpoints detailed in this section are as follows:

- **Continuous efficacy endpoints** including change from baseline in NPS and in NCS at Week 52, change from baseline in LMK score at Week 24, change from baseline in TSS, in Loss of Smell Symptom Severity score, in UPSIT score, in SNOT-22 total score and PROMIS SD-SF-8b score at Week 24 and Week 52: these endpoints will be analyzed in the same fashion as the co-primary endpoints described in [Section 9.2.2.2](#).
- **Proportion endpoints**, including proportion of participants with CRSwNP requiring SCS or surgery for CRS during the planned study intervention period and proportions of NPS responders, will be analyzed using an MH method stratified by asthma/AERD strata and region. The estimate of the MH weighted risk difference and corresponding Wald 95% confidence interval and Wald test using Sato variance will be provided. All data collected after study intervention discontinuation will be used in the analysis. Participants who discontinue the study without an event will be considered as no event.
- **Time to first SCS use or surgery for CRS** will be analyzed using a Cox regression model. The time to the first event will be included as the dependent variable while intervention group, asthma/AERD strata and region will be used as covariates. The HR will be estimated for comparison of each Itepekimab regimen to placebo. The Kaplan-Meier method will be used to derive the probabilities that a participant would experience an event up to specific time points for each intervention group.
- **The annualized number of SCS course or surgery for CRS** during the planned study treatment will be analyzed using a negative binomial regression model. The model will include the number of SCS course or surgery for CRS during the planned study treatment period as the response variable, with intervention group, asthma/AERD strata and regions. Log transformed treatment duration will be the offset variable. The estimated annualized number of SCS courses or surgery for CRS for each treatment group and its 95% CI will be derived from the negative binomial model. The event rate ratio of each Itepekimab regimen versus placebo and the corresponding 95% CI and p-values will be provided.

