- **Changes from baseline to Week 24 and 52 in pre-BD FEV1 and in ACQ-5 score** will be analyzed in participants with comorbid-asthma. These endpoints will be analyzed in the same fashion as for the coprimary endpoints without the asthma/AERD strata as a covariate in the model.
- **The following efficacy endpoints will be analyzed in participants with AERD**, in the same fashion as the one considered on the entire population without the asthma/AERD strata as a covariate in the model.
 - Change from baseline to Week 24 and 52 in NPS, NCS, pre-BD FEV1 and ACQ-5 score.
 - The proportion of participants requiring SCS or surgery for CRS during the planned study intervention period.
 - Annualized rate of SCS or surgery for CRS during the planned study intervention period.

- Time to first either SCS or surgery for CRS.

Other secondary endpoints analyses are defined in [Section 9.2.6.1](#) (AE, SAE), [Section 9.2.6.2](#) (laboratory abnormalities), [Section 9.2.7](#) (PK, immunogenicity).

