9.2.5 Multiplicity adjustment

Multiplicity is considered for the significance testing of multiple efficacy endpoints. The overall Type-I error rate will be controlled at the 2-sided 0.05 level.

As a nonbinding futility IA is planned for the study (see [Section 9.3](#)), an administrative penalty of $\alpha = 0.001$ will be taken from the significance level used at final analysis; that is, a 2-sided $\alpha = 0.049$ will be used for the final primary efficacy analysis. No further multiplicity adjustment will be performed for the IA.

At the final analysis, the family-wise Type I error rate for testing multiple hypotheses pertaining to the primary endpoint and secondary endpoints will be strongly controlled using a gate-keeping procedure. The procedure starts with testing the co-primary endpoints between 300 mg Q2W and placebo at the 2-sided 0.049 significance level. If both co-primary endpoints are significant, then the co-primary endpoints for 300 mg Q4W, the key secondary endpoints and a selective set of secondary endpoints including the efficacy endpoints on asthma and AERD sub-populations for both doses will be tested using a prespecified multiplicity testing procedure with the overall Type I error rate being controlled at 0.049 level among the multiple endpoints and the comparisons between each dose (300 mg Q2W or 300 mg Q4W) and placebo. The complete list of the endpoints and the multiplicity testing procedure will be specified in the SAP.

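### Section 9.2.3 carries the worst-possible-score rule over to pre-bronchodilator FEV1, which is measured in mL and has no worst possible score

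*Protocol*

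**What the plan says.** For the co-primary endpoints, Section 9.2.2.2 of the protocol handles two intercurrent events by a composite strategy: selected prohibited/rescue medication, and nasal/sinus surgery. The rule is "Data after the IE will be assigned to the worst possible score". Systemic corticosteroid use, stopping study treatment and other prohibited or rescue medication are handled by treatment policy.

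Section 9.2.3 passes this on by cross-reference. For FEV1 and ACQ-5 in participants with asthma it reads "These endpoints will be analyzed in the same fashion as for the coprimary endpoints", and the sentence goes on to drop the asthma/AERD factor from the model. The only exception is the covariate. The AERD analyses, FEV1 included, follow the same pattern.

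Table 2 lists "Change from baseline to Weeks 24 and 52 in pre-BD FEV1 (in mL) in participants with co-morbid asthma" and "Change from baseline to Weeks 24 and 52 in pre-BD FEV1 (in mL) in participants with AERD". Section 9.2.5 says that "a selective set of secondary endpoints including the efficacy endpoints on asthma and AERD sub-populations for both doses will be tested" within the type I error procedure. Table 3 sets out estimands for NPS and NCS only, so for FEV1 the cross-reference in Section 9.2.3 is the only text on intercurrent events.

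**The concern.** NPS and NCS are bounded scores with a defined worst value not far above the entry level. FEV1 is a volume. Section 8.2.6 (spirometry) gives no worst value, and nor does any other section. The analyst must either invent a number or take 0 mL, which describes nobody alive at the visit.

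Nasal surgery is a treatment failure for polyp size and congestion. It is not in itself a lung-function outcome. Section 6.9.1 has participants assessed as soon as possible after surgery with the end-of-treatment procedures, and Section 7.1.1 asks those who stop treatment to complete the remaining visits. Real FEV1 values after surgery may therefore exist, and the rule would replace them.

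At stake is the reading of small-subgroup endpoints that may be tested confirmatorily. With equal event rates an extreme imputed value costs power. With more events on placebo, it presents surgery counts as a lung-function benefit.

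**Working it through.** **The plan's own figure.** There is none for FEV1. The stated power for the co-primaries reproduces. For NPS, SE = 1.79 × √(2/70) = 0.303. With z = 1.969 for two-sided 0.049, power = Φ(1.10/0.303 − 1.969) = 0.95, as Section 9.4 says. This point does not touch the sample size.

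**Inputs from the protocol.** 70 per arm and alpha 0.049 (Section 9.4); about 65% with asthma and 25% with AERD (Section 4.1). Subgroup sizes: 70 × 0.65 = 45.5 and 70 × 0.25 = 17.5 per arm.

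**Assumed inputs (not in the protocol).** Baseline FEV1 2000 to 3000 mL with between-person SD 700 mL; SD of change 400 mL; mean change 0 on placebo; effect 200 mL; composite-event rates 2% to 10% per arm.

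**Distance to the worst value.** NPS is at least 5 at entry with maximum 8, so the rule moves a participant by at most 3 points, or 3/1.79 = 1.7 SD. FEV1 at 0 mL is 2000/400 = 5 to 3000/400 = 7.5 SD away.

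**One event.** For a participant otherwise at baseline, shift in the arm mean = baseline/n.
- Asthma: 2000/45.5 = 44 mL to 3000/45.5 = 66 mL.
- AERD: 2000/17.5 = 114 mL to 3000/17.5 = 171 mL.
- NPS, for comparison: at most 3/70 = 0.04 points against a planned difference of 1.10.

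**Two placebo events among 45, baseline 2500 mL.** p = 2/45. Taking both events at exactly 2500 mL:
- Mean shift = p × 2500 = 111 mL downward.
- Arm variance = (1−p) × 400² + p(1−p) × 2500² = 152,889 + 265,432 = 418,321, so SD = 647 mL instead of 400.
- SE of the difference = √((418,321 + 160,000)/45) = 113 mL, against √(2 × 160,000/45) = 84 mL without events.

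**Power in the asthma subgroup.** Each arm is a mixture: mean = (1−p)μ + pw; variance = (1−p)SD² + p·SD_b² + p(1−p)(w−μ)². Here w is minus the baseline mean and SD_b = 700 mL. Power = Φ(difference/SE − 1.969), without covariate adjustment.

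| Events per arm | Variance multiple | Power for 200 mL |
|---|---|---|
| none | 1.0 | 0.66 |
| 2% | 1.6–2.2 | 0.35–0.46 |
| 5% | 2.4–4.0 | 0.20–0.31 |

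With 10% events on placebo and 2% on active, the expected difference becomes 0.98 × 200 + (0.10 − 0.02) × baseline = 356 to 436 mL, for a true effect of 200 mL.

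**With a bounded rule.** Suppose 5% events per arm take a worst observed value averaging 300 mL below baseline (SD 300, assumed). The variance multiple is 1.03 and power about 0.60.

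**ACQ-5, where the worst value of 6 is defined.** Assume baseline 1.6, SD of change 1, SD_b 1.1, placebo change −0.2, effect 0.6, and 5% events per arm. The variance multiple is about 2.2 and power falls from 0.81 to 0.45.

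**The case against.** Section 9 calls itself a summary and leaves technical detail to the SAP, which may give FEV1 its own rule. A composite strategy is a legitimate choice, and surgery also ends study treatment. The protocol speaks of a score and nowhere assigns 0 mL. It gives no composite-event rate either; the figure below 5% in Section 9.4 is dropout.

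Part of this stands. The 0 mL results show what the only literal bound would do, not what the sponsor plans, and their size is assumed throughout. The appeal to the SAP does not remove the point: Section 9.2.3 does not leave the matter open but fixes the co-primary approach and names one exception, which is not this one.

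A reader might also infer that the rule damages every continuous secondary endpoint, and more so on wider scales. The documents do not support that. SNOT-22, UPSIT and Lund-Mackay have stated ranges, so a worst score exists and the composite rule can be applied. What drives the effect is distance to the worst value in SD units and the event rate, not scale width. At 5% events per arm, under assumed baselines and SDs, variance rises by a factor of only 1.16 for UPSIT (0–40) and 1.12 for Lund-Mackay (0–24), and by 1.7 for SNOT-22, all less than for ACQ-5 (0–6). With 10% placebo and 2% active events, SNOT-22 power goes up, from 0.94 to 0.975.

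**Conclusion.** The point holds for FEV1, in both the asthma and the AERD analyses: the protocol prescribes a value that does not exist for this measurement. Read as 0 mL, one event moves an arm mean by about 44 to 66 mL (asthma) or 114 to 171 mL (AERD). The bias can run either way, depending on which arm has more events. These figures rest on an assumed baseline of 2000 to 3000 mL; the power figures also rest on an assumed SD, effect and event rate.

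ACQ-5 is a lesser case: the rule is defined there, but it assigns the worst asthma control because of nasal surgery and may roughly double the variance. For NPS, NCS, SNOT-22, UPSIT, Lund-Mackay, TSS, smell and PROMIS, the rule is an acceptable choice of estimand.

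**What to change.** In Section 9.2.3, exempt pre-bronchodilator FEV1 (asthma and AERD) from the worst-possible-score rule and name the replacement. Section 9.2.2.4 already contains both tools, as supplementary analyses of the co-primaries:
- after nasal/sinus surgery, treatment policy, using the FEV1 observed;
- after selected prohibited biologics, the worst observation carried forward, meaning the participant's worst observed FEV1.

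Consider the same for ACQ-5. Keep the composite rule for the other bounded scores; worst observation carried forward is optional there as a supplementary analysis. For Lund-Mackay and UPSIT at Week 24 it would mostly carry baseline forward, since the schedule has no assessment in between.

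The cost is a few lines, to be settled before unblinding. The FEV1 estimand will then differ from the co-primary estimand and should be stated as such. Spirometry is scheduled only at Weeks 0, 4, 24 and 52 during treatment, so before Week 24 the worst observed value comes from few measurements. The text should say which visits count.

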4 STUDY DESIGN

4.1 OVERALL DESIGN

This is a Phase 3, multicenter, randomized, double-blind, placebo-controlled, parallel-group, 3-arm study to assess the efficacy, safety, and tolerability of 2 different dosing regimens of SC itepekimab in adult participants with inadequately-controlled CRSwNP on background of INCS.

This study will include adult participants (≥ 18 years of age) with bilateral nasal polyposis and chronic symptoms of sinusitis despite previous surgery and/or treatment with SCS. Participants are required to have a bilateral endoscopic NPS of at least 5 out of a maximum of 8, with a score of at least 2 for each nostril; manifest symptoms of nasal blockade/obstruction/congestion with a NCS at Screening of at least 2 (0-3 scale); and manifest at least 1 out of the following 2 symptoms at screening: (1) anterior or posterior rhinorrhea; (2) reduction or lost sense of smell.

All eligible participants will be randomized in 1:1:1 ratio (approximately 210 participants in total) and treated for 52 weeks, receiving SC administrations of itepekimab or placebo according to the following dosing schedules:

- Itepekimab 300 mg, administered as a single SC injection Q2W.
- Itepekimab 300 mg, administered as a single SC injection Q4W with alternating SC injection of matching placebo at the 2-week interval between active IMP.
- Placebo, administered as a single SC injection of matching placebo to itepekimab Q2W.

Itepekimab will be administered as an add-on therapy to MFNS. In Japan, participants on INCS (MFNS or other INCS) will continue taking their daily INCS with a stable dose through all periods of the study. In Japan, participants not on INCS prior to screening, will receive MFNS during screening and throughout the study. In China, participants will continue their stable daily dose of INCS which may include MFNS during the screening period and throughout the study.

The co-primary endpoints are changes from baseline to Week 24 in NPS and NCS in the itepekimab-treated participants compared to placebo. NPS is assessed based on nasal endoscopy performed locally by the Investigator and centrally read for scoring.

Randomization will be stratified by asthma/AERD status (no asthma, asthma only, asthma & AERD), and region (Asia or rest of the world). This study will aim to enroll approximately 65% of participants with co-morbid asthma, and approximately 25% participants with AERD.

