6.3 ASSIGNMENT TO STUDY INTERVENTION

All participants will be centrally assigned to randomized study intervention using an IRT. Before the study is initiated, the telephone number and call-in direction for the Interactive Voice Response System (IVRS) and/or the log in information and direction for the Interactive Web Response System (IWRS) will be provided to each site.

Definition of a randomized participant is a participant from screened population who has been allocated to a randomized intervention regardless of whether the intervention was received or not. A participant cannot be randomized more than once in the study. The randomized intervention kit number list is generated centrally by Sanofi. The IMPs are packaged in accordance with this list. Study intervention will be dispensed at the study visits as summarized in the SoA ([Section 1.3](#)).

During the randomization process, participants will be stratified by asthma/AERD status (no asthma, asthma only, asthma & AERD), and region (Asia or rest of the world).

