9.4 SAMPLE SIZE DETERMINATION

Approximately 210 participants will be randomized in 1:1:1 ratio to investigational intervention groups.

The sample size calculations are based on the co-primary endpoints NPS and NCS. The planned sample size is approximately 70 participants per study intervention group. With a two-sample t-test at a two-sided significance level of $\alpha = 0.049$, this sample size will provide:

- 95% power to detect a -1.10 difference for change from baseline in NPS at Week 24 between itepekimab and placebo and a common SD of 1.79. The minimal detectable difference is around -0.60.
- 95% power to detect a -0.55 difference for change from baseline in NCS at Week 24 between itepekimab and placebo and a common SD of 0.9. The minimal detectable difference is around -0.30.

The combined power of the 2 co-primary efficacy endpoints is at least 90% assuming no negative correlation between the 2 endpoints.

Differences of -1.10 and -0.55 in NPS and NCS from placebo are considered clinically relevant (54). The common SDs were estimated from LIBERTY NP SINUS-24 and SINUS-52 trials with dupilumab (NCT02912468; NCT02898454).

For the key secondary endpoints of change from baseline in NPS and NCS at Week 52, the study will have a 95% power to detect the same treatment differences as for the co-primary endpoints with the same assumed common SDs based on a two-sided α level of 0.049.

Note that as the primary analyses will be performed based on the ITT population with the dropouts (ie, one of the intercurrent events) handled using the treatment policy strategy and missing data imputed using the MI method, the sample size calculations were performed on all randomized participants. In other words, the detectable treatment differences stated above are for ITT population including early dropouts. Very low dropout rates (<5%) were observed from LIBERTY NP SINUS-24 and SINUS-52 studies (NCT02912468; NCT02898454), therefore the impact on the treatment effects is expected to be minimal.

Calculations were made based on two-sample t-test using nQuery Advisor 9.2.1.0.

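### The FEV1 and ACQ-5 models in participants with asthma drop a stratification factor that still has two levels there: a minor, avoidable loss of efficiency

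*Protocol*

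**What the plan says.** Under Protocol section 6.3, "participants will be stratified by asthma/AERD status (no asthma, asthma only, asthma & AERD), and region (Asia or rest of the world"). The co-primary ANCOVA in section 9.2.2.2 follows the randomization: it has "randomization stratification factors (asthma/AERD status and regions) as fixed effects, and the baseline value as covariates". In section 9.2.3 the full-population Mantel-Haenszel, Cox and negative binomial analyses also use the asthma/AERD strata and region.

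The asthma endpoints depart from this. Section 9.2.3 states that changes to Weeks 24 and 52 in pre-BD FEV1 and ACQ-5 "will be analyzed in participants with comorbid-asthma", by the co-primary method but "without the asthma/AERD strata as a covariate in the model". The next bullet gives the AERD-subgroup analyses the same exclusion: they are done "in the same fashion as the one considered on the entire population without the asthma/AERD strata as a covariate in the model".

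No reason is given for the exclusion in the asthma subgroup, and nothing else in the protocol restores the factor. Section 9.2.5 names efficacy endpoints in the asthma and AERD subpopulations as part of the set tested under type I error control. It leaves the complete list to the SAP.

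**The concern.** The two exclusions look alike, but the subgroups differ. Among participants with AERD only one level of the factor exists, so it cannot be fitted and has to go. Among participants with asthma, two of the three levels used at randomization are still present.

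When randomization is stratified on a factor related to outcome, the arms are balanced on it by design. A model that omits the factor leaves the between-stratum variation in the residual. The reported standard error then takes no credit for the balance. The synopsis describes patients with both asthma and AERD as having more severe disease that is harder to control, so some relation to outcome is plausible. At stake is a little precision in endpoints that may be tested under type I error control.

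This is not a matter left open for the SAP. The protocol prescribes the removal, so a SAP that kept the factor would contradict it.

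**Working it through.** **The plan's own figures.** Section 9.4 gives power only for the co-primary endpoints, not for FEV1 or ACQ-5. With 70 per arm, two-sided alpha 0.049 and a two-sample t-test, the stated 95% reproduces: 95.0% for NPS (difference 1.10, SD 1.79) and 94.8% for NCS (difference 0.55, SD 0.9). Those figures are sound but do not bear on the asthma models, which need a separate calculation.

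**Inputs**
- Section 9.4: "Approximately 210 participants will be randomized in 1:1:1 ratio to investigational intervention groups".
- Section 4.1: the study aims for "approximately 65% of participants with co-morbid asthma, and approximately 25% participants with AERD". Both percentages are of all participants.
- Two-sided alpha 0.049, from section 9.2.5.
- Assumed: d, the difference between asthma & AERD and asthma only in the endpoint after adjustment for baseline, in residual SDs. The protocol gives no value. The range used is 0 to 0.5.
- Assumed: the 25% AERD target is met by participants in the asthma & AERD stratum.

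**Subgroup size.** Asthma: 0.65 × 210 = 136.5, or 45.5 per arm. Asthma & AERD: 0.25 × 210 = 52.5. Asthma only: 136.5 − 52.5 = 84. The AERD share within asthma is p = 0.25/0.65 = 0.385, so p(1−p) = 0.2367.

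**Inflation of the model SE.** Omitting a balanced two-level factor multiplies the residual variance by 1 + p(1−p)d², and so the SE by f = √(1 + 0.2367d²).

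**Power.** Take an effect that has 80% power under the model with the factor. Its standardised size is 1.969 + 0.842 = 2.810. Treating the inflated SE as if it were also the true SE, power is Φ(2.810/f − 1.969).

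| d | p(1−p)d² | SE inflation | Power |
|---|---|---|---|
| 0 | 0 | 0% | 80.0% |
| 0.2 | 0.0095 | 0.5% | 79.6% |
| 0.3 | 0.0213 | 1.1% | 79.2% |
| 0.5 | 0.0592 | 2.9% | 77.7% |

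These power figures are the pessimistic end. With stratified randomization the estimator itself does not become more variable; only its reported SE grows. Power is then Φ(2.810 − 1.969f), which gives 79.7%, 79.4% and 78.4% at d = 0.2, 0.3 and 0.5.

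**Simulation check.** ANCOVA was fitted with and without the factor to 136 participants (84 and 52), randomized in permuted blocks within stratum, with 20,000 runs per value of d.

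| d | True SE, omitted / kept | Mean model SE, omitted / kept | Type I error at 0.049, omitted / kept |
|---|---|---|---|
| 0 | 0.209 / 0.209 | 0.2104 / 0.2104 | 0.048 / 0.048 |
| 0.2 | 0.210 / 0.210 | 0.2115 / 0.2104 | 0.048 / 0.049 |
| 0.5 | 0.209 / 0.209 | 0.2166 / 0.2104 | 0.041 / 0.046 |

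The Monte Carlo error of each type I error rate is about √(0.049 × 0.951/20,000) = 0.0015. The true SE is the same in both models. Without the factor the model SE is too large and the test falls below its nominal level.

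**The case against.** The strongest reply is that this is a permissible modelling choice of little consequence. The estimate is unbiased and the type I error does not exceed its nominal level. The model still adjusts for baseline, which should absorb much of any difference in starting severity. The synopsis statement on AERD is qualitative, belongs to the CRSwNP rationale, and says nothing about change in FEV1 or ACQ-5. If the remaining difference is near zero, nothing is lost. All of this stands, and it limits the size of the point. It does not supply a reason to drop a factor that the trial randomizes on and that the full-population models keep.

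Three stronger readings are tempting but unsupported:

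- **Chance AERD imbalance goes uncorrected and distorts the comparison.** Stratifying on this factor is what limits such imbalance. Only residual imbalance from incomplete blocks or missing data could remain, and the documents give no basis for sizing it.
- **The omission costs as much information as losing a sizeable number of participants.** That equivalence describes the reported SE, not the true variability of the estimate, which hardly changes. A large loss also needs a residual difference well above 0.5 SD, for which the documents offer no support.
- **The exclusion was carried over by mistake from the AERD analyses.** The wording is shared, but nothing in the protocol shows how it arose.

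The confirmatory weight is also only partly settled, because the SAP decides which asthma endpoints and time points are tested.

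**Conclusion.** The point holds as a minor one. Section 9.2.3 removes the asthma/AERD factor from the asthma-subgroup FEV1 and ACQ-5 models although two randomization levels remain, and it gives no reason. The consequence is a somewhat overstated standard error and a conservative test, with no bias and no excess of false positives. For a residual difference of up to 0.5 SD the SE inflation stays under 3%, and an 80% power falls by at most about 2.3 percentage points (80 − 77.7).

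This size rests on the assumed range of d and on the enrolment targets being met. Section 2.2 describes both shares as approximate minimums, so the mix may differ. The reading of the text is certain; the magnitude is not, and it could be nil.

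**What to change.** In section 9.2.3, state that the FEV1 and ACQ-5 models for participants with comorbid asthma include treatment, region, baseline and a two-level factor, asthma only versus asthma & AERD. Confine the exclusion of the asthma/AERD factor to the AERD-only analyses, and carry the same wording into the SAP.

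The cost is one degree of freedom and a change of wording. The stratum is already recorded at randomization, so no new data are needed, and neither the sample size nor the testing procedure changes.
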